7.2 DATA QUALITY ASSURANCE

The Sponsor performs quality control and assurance checks on all of its clinical studies.

Section [7.4](#) provides details regarding study monitoring procedures.

The study may be subject to audit by the Sponsor, its representatives, or regulatory authorities. In the event of an audit, the Investigator must agree to allow the Sponsor, representatives of the Sponsor, or the FDA or other regulatory agencies access to all study records.

7.3 ELECTRONIC CASE REPORT FORMS AND DATA MANAGEMENT

Study data will be recorded in the patient's source documentation and entered in eCRF in the Sponsor or designee's electronic data capture (EDC) system. Source documentation supporting the eCRF data should indicate the patient's participation in the study and should document the dates and details of study procedures, AEs, all observations, and patient status. The Investigator is responsible for verifying that all data entries on the eCRFs are accurate and correct and ensuring that all data are entered in a timely manner, as soon as possible after the information is collected. An explanation should be provided for any missing data. The Investigator must provide through the EDC system his or her formal approval of all the information in the eCRFs and changes to the eCRFs to endorse the final submitted data for each patient.

The Sponsor will retain the final eCRF data and corresponding audit trails. A copy of the final archival eCRF in the form of a compact disc or other electronic media will be placed in the Investigator's study file.

A record of screen failures and pretreatment failures will be maintained for patients who do not qualify for enrollment, including the reason for the failure.

7.4 STUDY MONITORING

The Sponsor performs quality control and assurance checks on all of its clinical studies. Before any patients are enrolled in the study, a representative of the Sponsor or its authorized designee will meet with the Investigator and his/her staff to review relevant and important study-related information including, but not limited to, the protocol, the Investigator's Brochure, the eCRFs and instructions for their completion using the EDC system, the procedure for obtaining informed consent, and the procedure for reporting AEs and SAEs.

A Sponsor representative, the Clinical Site Monitor, will monitor the progress and conduct of the study by periodically conducting monitoring visits and by frequent communications (telephone, e-mail, letter, and fax) with the study sites. The site monitor will ensure that the study is conducted according to the protocol and regulatory requirements. During monitoring visits, the information recorded on the eCRFs will be verified against source documents. Upon request of the monitor, auditor, IRB/IEC, or regulatory authority, the Investigator should make all requested study-related records available for direct access.

All aspects of the study will be carefully monitored by the Sponsor or its designee for compliance with applicable government regulations with respect to GCP and current standard operating procedures.

8. STUDY SPONSORSHIP

8.1 INVESTIGATOR AND STUDY TERMINATION

The Sponsor may terminate Investigator participation at any institution for any reason. If participation is ended at the site by either the Sponsor or the Investigator, the Investigator must:

- Return all study medications and any study materials to the Sponsor
- In cases where the Investigator opts to self-terminate, provide a written statement describing why the study was terminated prematurely

The Sponsor may terminate the study in its entirety or at a specific center at any time for any reason, including but not limited to the following:

- Failure to enroll patients
- Protocol violations
- Inaccurate or incomplete data
- Unsafe or unethical practice
- Questionable safety of the study medication
- Suspected lack of efficacy of the study medication
- Administrative decision

8.2 REPORTING AND PUBLICATION

All data generated in this study will be the property of the Sponsor. Study report(s) will be prepared at the completion of the study.

Publication of the results by the Investigator will be subject to agreement between the Investigator and the Sponsor.

9. INVESTIGATOR OBLIGATIONS

9.1 PERFORMANCE

The Investigator must demonstrate reasonable efforts to obtain qualified patients for the study. The Sponsor may terminate the study with any Investigator for Investigator nonperformance or Investigator noncompliance.

9.2 USE OF INVESTIGATIONAL MATERIALS

The Investigator will acknowledge that the drug supplies are investigational and as such must be used strictly in accordance with the protocol and only under the supervision of the Investigator or subinvestigators. Study medication must be stored in a safe and secure temperature-monitored location. The Investigator must maintain adequate records documenting the receipt and disposition of all study supplies. The study site must record the date the study medication was received and maintain a dispensing record in which to record each patient's use. A complete reconciliation of study medication will be performed at the site close-out visit with a final accountability report provided to the Sponsor as part of the site close-out report. Written instructions for return of all unused and reconciled study medication to an appropriate waste handler will be provided before the end of the study. No study medication may be destroyed by study site without prior written permission of the Sponsor.

9.3 RETENTION AND REVIEW OF RECORDS

Records and documents pertaining to the conduct of this study, including eCRFs, source documents, ICFs, laboratory test results, and medication inventory records, must be retained by the Investigator in accordance with locally applicable regulatory requirements; and, in any event, for a minimum period of 5 years and in accordance with the clinical site's contract for this study.

No study records shall be destroyed without notifying Sponsor and giving Sponsor the opportunity to take such study records or authorizing in writing the destruction of records after the required retention period.

If the Investigator retires, relocates, or otherwise withdraws from the responsibility of keeping the study records, custody must be transferred to another person (the Sponsor, IRB/IEC, or other

Investigator) who will accept the responsibility. The Sponsor must be notified of and agree to the change.

9.4 PATIENT CONFIDENTIALITY

All data collected in the context of this study will be stored and evaluated in such a way as to guarantee patient confidentiality in accordance with the legal stipulations adopted by local jurisdictions applying to confidentiality of data. All patient records will be identified only by patient identification number. Patient names are not to be transmitted to the Sponsor or its authorized designee. The Investigator will keep a Master Patient List on which the patient identification number and the full name, address, and telephone number of each patient is listed.

APPENDIX 1 PROHIBITED MEDICATIONS, SUPPLEMENTS, AND FOODS

Prohibited from the Run-in Visit (Day -14 to Day -17) through the duration of the study:

- Specific inhibitors of PDE5 including sildenafil, tadalafil, vardenafil
- All supplements for the treatment of erectile dysfunction
- Nonspecific inhibitors of PDE 5 including dipyridamole, theophylline
- Other sGC stimulators, including riociguat
- Nitrates including nitroglycerin, isosorbide mononitrate, isosorbide dinitrate, sodium nitroprusside, amyl nitrate
- Other NO donors in any form, including beetroot
- P2Y12 inhibitors including prasugrel, clopidigrel
- Aspirin ≥ 325 mg/day
- Any anticoagulant medication
- [REDACTED]

[REDACTED]

[REDACTED]

[REDACTED]

[REDACTED]

[REDACTED]

[REDACTED]

## 1. Glossary of Abbreviations

Abbreviation	Description
AE	Adverse Event
ANCOVA	Analysis of Covariance
ASCQ-Me	Adult Sickle Cell Quality of Life Measurement Information System
ATC	Anatomical Therapeutic Chemical
BLQ	Below Assay's Limit of Quantification
BMI	Body Mass index
BP	Blood Pressure
CI	Confidence Interval
CMH	Cochran-Mantel-Haenszel
CTCAE	Common Terminology Criteria for Adverse Events
CV	Coefficient of Variation
DMC	Data Monitoring Committee
ECG	Electrocardiogram
eCRF	Electronic Case Report Form
eDiary	Electronic Diary
EOT	End of Treatment
EQ-5D-5L	Euro QOL 5-Dimension 5-Level
F/U	Follow UP
HU	Hydroxyurea
ICF	Informed Consent Form
ICH	International Council on Harmonisation
IQR	Interquartile Range
ITT	Intent to Treat
IW-1701	olinciguat
LSM	Least-Squares Mean
MCS	Mental Component Summary
MedDRA	Medical Dictionary for Regulatory Activities
NRS	Numerical Rating Scale
olinciguat	IW-1701

This document is confidential.

Abbreviation	Description
PCS	Physical Component Summary
PD	Pharmacodynamic(s)
PGI-C	Patient Global Impression of Change
PGI-S	Patient Global Impression of Severity
PK	Pharmacokinetic(s)
PRO	Patient-Reported Outcome
PROMIS	Patient-reported Outcomes Measurement Information System
PT	Preferred Term
QD	Once Daily
QTcF	QT Interval Corrected for Heart Rate using Fridericia's Formula
SAE	Serious Adverse Event
SAP	Statistical Analysis Plan
SAS	Statistical Analysis System
SCD	Sickle Cell Disease
SCD-SAF	Sickle Cell Disease – Symptom Assessment Form
SD	Standard Deviation
SEM	Standard Error of Mean
SF-12v2	Short-Form Health Survey 12, Version 2
SI	Standard International System of Units
SOC	System Organ Class
SOP	Standard Operating Procedure
TEAE	Treatment-Emergent Adverse Event
TFLs	Tables, Figures and Listings
VAS	Visual Analog Scale
VOC	Vaso-occlusive Crisis
WHO	World Health Organization

This document is confidential.

## 2. Purpose

This statistical analysis plan (SAP) describes the planned analysis of the safety, tolerability, efficacy and PK data from Study C1701-202, a randomized, placebo-controlled, Phase 2 study to evaluate the safety and pharmacodynamics of once-daily (QD) oral olinciguat (IW-1701) in participants with stable sickle cell disease (SCD). A detailed description of the planned tables, figures, and listings (TFLs) to be presented in the clinical study report (CSR) is provided in the accompanying TFL shell document.

Note: Throughout this SAP, reference to “IW-1701” is replaced by its international nonproprietary name (olinciguat), where possible.

The intent of this document is to provide additional detailed guidance for the planned statistical analyses of the safety, tolerability, efficacy and PK data as defined in the study protocol. Any changes to the protocol planned analyses must be agreed upon between Cycleron [REDACTED] and documented under [Section 11](#) (Changes from Analysis Planned in Protocol).

This SAP must be finalized prior to locking of the clinical database for this study. When the SAP and TFL shells are agreed upon and finalized, they will serve as the template for the analyses presented in this study’s CSR, along with the final version of the protocol, as applicable. This SAP supersedes the statistical considerations identified in the protocol; where considerations are substantially different, they will be so identified. If additional analyses are required to supplement the planned analyses described in this SAP, they may be performed and will be identified in the CSR. Any substantial deviations from this SAP will be agreed upon between Cycleron [REDACTED] and identified in the CSR.

### 2.1. Responsibilities

[REDACTED] perform the statistical analyses and is responsible for the production and quality control of all tables, figures and listings; the full population pharmacokinetic (PK) analysis will be provided in a separate PK analysis report which will be provided by a different vendor; only the PK plasma concentrations (see [Section 9](#)) will be summarized under this SAP.

### 2.2. Timings of Analyses

The final analyses of safety and pharmacodynamics is planned after all participants have either completed the final study visit or terminated early from the study and the data processing has been completed, and the study database has been locked.

This document is confidential.

### 3. Study Objectives

#### 3.1. Study Objectives and Endpoints

Table 1 provides the study objectives and the corresponding endpoint(s) that will be summarized and analyzed to determine if the objective is met.

Table 1: Study objectives and corresponding endpoints

Objective	Endpoint
	Primary
The primary objective is to assess the safety and tolerability of oral, once-daily (QD) olinciguat when administered for approximately 12 weeks to participants aged 16 to 70 years with sickle cell disease (SCD).	Incidence (number and percentage of patients) and frequency (number of events) of treatment-emergent adverse events (TEAEs) Incidence of TEAEs by severity Incidence of study drug-related TEAEs
Exploratory Patient-reported Outcomes	
To evaluate the effect of oral, once-daily olinciguat on symptoms of SCD, health-related quality of life, and biomarkers when administered for approximately 12 weeks to participants aged 16 to 70 years with SCD	Change from baseline in Sickle Cell Disease – Symptom Assessment Form (SCD-SAF) total score at Weeks 4, 8, 12, and End of Treatment (EOT) Pain as measured on the 11-point numerical rating scale (NRS) by week and for the overall Treatment Period Percent change from baseline in pain as measured on the 11-point NRS by week and for the overall Treatment Period Change from baseline in pain as measured on the 11-point NRS by week and for the overall Treatment Period Change from baseline in fatigue as measured on the 11-point NRS by week and for the overall Treatment Period Change from baseline ASCQ-Me pain impact score
Exploratory Pharmacodynamics	
To evaluate the effect of oral, once-daily olinciguat on symptoms of SCD, health-related quality of life, and biomarkers when administered for approximately 12 weeks to participants aged 16 to 70 years with SCD	Change from baseline in hemoglobin at Weeks 4, 8 and 12 Proportion of patients with change from baseline in hemoglobin $\geq 1$ g/dL at end of treatment Change from baseline in fetal hemoglobin at Weeks 4, 8 and 12
Exploratory Pharmacokinetics	
To evaluate the pharmacokinetics (PK) of oral, once-daily olinciguat when administered for approximately 12 weeks to participants aged 16 to 70 with SCD	Plasma concentrations of olinciguat at assessed timepoints

Note: Bolded parameters associate directly with corresponding endpoint(s).

This document is confidential.

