4. STUDY ENDPOINTS

4.1 PRIMARY ENDPOINTS

4.1.1 Safety

- Incidence, frequency, and severity of TEAEs and study drug-related TEAEs in IW-1701-treated patients compared with placebo-treated patients over the study

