### 3.2. Brief Description

This Phase 2, multicenter, randomized, double-blind, placebo-controlled, parallel-group study with a 2-week single-blind Run-in Period will evaluate the safety and pharmacodynamics (PD) of oral olinciguat compared with placebo when administered QD for approximately 12 weeks in participants with SCD.

At the Screening Visit, participants will undergo preliminary procedures to determine their initial eligibility. At the Run-in Visit (which will occur at least 3 calendar days after the Screening Visit), eligible participants will then begin 14 to 17 days of single-blind placebo dosing and will begin recording their daily and weekly symptom assessments in an electronic diary (eDiary).

On Day 1 of the Treatment Period, participants who continue to be eligible will be randomized to double-blind study drug (QD olinciguat or placebo). Note that participants enrolled under protocol Amendment 3 or earlier were randomized differently than those randomized under Amendment 4 and later, as described below.

- Under Amendment 3 or earlier: Participants were randomly assigned in a 1:1:1:1 ratio to placebo, 2 mg olinciguat, 4 mg olinciguat, or 6 mg olinciguat (see [Table 3](#))
- Under Amendment 4 and later: Participants were randomly assigned in a 3:1 ratio to 18 mg olinciguat or placebo (see [Table 4](#))

On Day 1 and for each up-titration visit, participants must remain in the clinic at least 6 hours postdose and will be allowed to leave thereafter at the Investigator's discretion.

At all scheduled study visits, participants will undergo safety, efficacy, and PK assessments and, as applicable, will take the relevant study drug dose and will be issued study drug supply for subsequent at-home QD dosing. In addition, participants will receive scheduled phone calls in between the scheduled visits to monitor TEAEs and concomitant medications and procedures. Throughout the Treatment Period, participants will continue completing the patient-reported outcome (PRO) questionnaires each day in their eDiary.

Beginning in March 2020, remote visits via phone call have been allowed to accommodate the impact of COVID-19 on study visits and participants' safety. The phone visits, when necessary, have been utilized to collect adverse event, concomitant medication, select vital sign timepoints, uptritration eligibility, and other relevant data.

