### 3.4. Determination of Sample Size

For this Phase 2 study, an overall sample size of approximately 88 participants is planned. Of these participants, approximately 40 are expected to be randomized under Protocol Amendment 3 or earlier and approximately 48 participants are expected to be randomized under Amendment 4 and later (see [Section 3.5](#)). The sample size was determined outside of statistical considerations and is considered reasonable based on precedent set by prior studies of similar nature and design.

This document is confidential.

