### 7.1. Study Drug Exposure and Compliance

Exposure to study drug, calculated as the number of days from the first dose taken post-randomization to the date of the last dose taken, inclusive, will be summarized as both categorical variable (based on different lengths) and numeric variable, by treatment group for the Safety Population. Patient years (defined as total treatment duration in days for a specific treatment group divided by 365.25) will be also derived for participants by treatment group.

The total number of tablets taken between specified visits and overall for the entire study will be calculated for each participant. Treatment compliance will be based on the number of tablets expected to be taken.

$$\text{Compliance (\%)} = 100 \times \frac{\text{Number of Tablets Taken}}{\text{Number of Tablets Expected to be Taken}}$$

The number of tablets taken will be calculated as (total number dispensed – total number lost – total number returned). If the number of tablets lost is missing or unknown, the number lost will be estimated as zero. Compliance will not be calculated if dispensed number or returned number is missing.

Percent compliance for study drug will be summarized by treatment group for each scheduled visit and overall for the Safety Population. Compliance rates will also be categorized as ' $<80\%$ ', ' $80\%-120\%$ ', and ' $>120\%$ ', and summarized by treatment group.

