### 7.2. Adverse Events

AEs will be coded using the MedDRA Version 20.0 or later and will be classified by MedDRA SOC and PT.

AEs are collected from date of signed informed consent form (ICF) through the last Follow-up Visit. TEAEs, SAEs, and on-therapy SAEs are defined in [Section 5.2.4](#). Pre-treatment AEs during Screening are defined as AEs started on/after Screening Visit and before the first dose of Run-in placebo. Pre-treatment AEs during Single-blind Run-in Period are defined as AEs started on/after the first dose of Run-in placebo and before the first dose of randomized study drug.

The number and percentage of participants who experience at least 1 TEAE as well as those who experience each specific SOC and PT will be presented by treatment group for the Safety Population. For presentation of AE incidence, AEs will be sorted by SOC, and within each SOC, by PT in the decreasing incidence of the last column of summary table, and then the column before it one by one. AEs will also be presented by severity (CTCAE v.4.03; Grade 1–Grade 5). For AEs that change severity ratings, the AE will be included only once in the summaries, under the maximum severity rating assigned by the Investigator. Additionally, TEAEs and SAEs occurring in the first, second, and fifth week of the double-

This document is confidential.

blind Treatment Period will be listed separately to distinguish among any effects of the initial dose (Week 1), the up-titrated dose (Week 2), and the further up-titrated dose (Week 5).

AEs occurring during Screening and the Single-blind Run-in Period will be summarized and listed separately.

More specifically, the following summary tables will be provided:

1. Overall Summary of TEAEs
2. Incidence of TEAEs by SOC and PT
3. Incidence of TEAEs by SOC, PT, and severity
4. Incidence of TEAEs by SOC, PT and relationship to double-blind study drug
5. Incidence of on-therapy SAEs by PT
6. Incidence of AEs leading to study drug discontinuation by PT
7. Incidence of pre-treatment AEs during Screening by SOC and PT (Screened Population)
8. Incidence of pre-treatment AEs during Single-blind Run-in Period by SOC and PT (Single-blind Run-in Population)
9. Incidence of adverse events of special interest (AESIs) by PT
10. Incidence of TEAEs by SOC, PT, and region (US vs. Lebanon)
11. Incidence of VOCs by PT
12. Summary of VOC events by location (eg, extremity) and outcome (eg, acute chest syndrome)

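### The primary safety endpoint includes a raw number of TEAEs per arm, but arm sizes range from about 10 to 36 and no AE output named in the SAP scales the count by exposure

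*SAP*

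**What the plan says.** SAP 3.1, Table 1, gives the primary endpoint an incidence part (number and percentage of patients) and a second part, the "frequency (number of events) of treatment-emergent adverse events (TEAEs"). Protocol 4.1.1 makes the endpoint comparative: incidence, frequency and severity "in IW-1701-treated patients compared with placebo-treated patients over the study".

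The arms differ in size by design. Under Amendment 3 or earlier, "Participants were randomly assigned in a 1:1:1:1 ratio to placebo, 2 mg olinciguat, 4 mg olinciguat, or 6 mg olinciguat"; under Amendment 4 and later, "Participants were randomly assigned in a 3:1 ratio to 18 mg olinciguat or placebo" (both SAP 3.2). SAP 5.1 shows placebo in three columns: PBO1 (Amendment 3 or earlier), PBO2 (Amendment 4 or later) and Overall.

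On exposure, SAP 7.1 says that patient years, meaning total treatment days "divided by 365.25) will be also derived for participants by treatment group". SAP 7.2 then describes the TEAE output as "The number and percentage of participants who experience at least 1 TEAE", with breakdowns by SOC, PT, severity and relationship. Its list of 12 summary tables names none per patient or per patient-year. SAP 5.2.4 counts TEAEs from the first randomized dose to 7 days after the last dose, and on-therapy SAEs to 28 days after the final dose. The only event rate that the SAP scales by exposure is the annualized VOC rate in section 8.2.1, an exploratory endpoint.

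**The concern.** A number of events can be compared between arms only if the arms have similar total time at risk. Here they do not, for two separate reasons. One is certain: allocation gives the 18 mg arm three times the patients of its concurrent placebo. The other is possible: a patient who stops early leaves the TEAE window 7 days later and contributes less time in which events can be counted. Dividing by N removes the first effect but not the second.

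The two effects push the 18 mg count in opposite directions, so the count cannot be read at face value. What is at stake is one component of the primary endpoint, which as defined would largely reflect arm size and exposure. The SAP already applies the remedy to VOCs, and it derives patient-years that no AE output named in its text uses.

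**Working it through.** **Inputs.** SAP 3.4 gives the planned size of each stage. For the first stage, "approximately 40 are expected to be randomized under Protocol Amendment 3 or earlier". The second stage plans about 48. Allocation ratios are from SAP 3.2. Planned treatment is about 85 days (Protocol 3.1, end-of-treatment visit on Day 85). The TEAE window adds 7 days (SAP 5.2.4), so planned time at risk is 85 + 7 = 92 days per completer.

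**Plan's own figure.** 40 + 48 = 88, which matches the stated overall sample size. The documents give no power calculation, expected TEAE rate or discontinuation rate to reproduce.

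**Arm sizes.** 18 mg: 48 × 3/4 = 36. PBO2: 48 × 1/4 = 12. Each Amendment 3 arm, including PBO1: 40/4 = 10. Overall placebo: 12 + 10 = 22.

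**Effect of allocation alone.** Expected count = rate × N × time at risk. With equal rate and time at risk, the count ratio is the ratio of the Ns:

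| Comparison | Count ratio with no drug effect |
|---|---|
| 18 mg vs PBO2 | 36/12 = 3.0 |
| 18 mg vs Overall placebo | 36/22 = 1.64 |
| 18 mg vs each low-dose arm | 36/10 = 3.6 |
| Each low-dose arm vs Overall placebo | 10/22 = 0.45 |

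These ratios do not depend on the event rate. As an illustration, an assumed 10 TEAEs per patient-year gives 10 × 36 × 92/365.25 = 90.7 events on 18 mg, 30.2 in PBO2 and 55.4 in Overall placebo. Divided by time at risk, every ratio returns to 1.00.

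**Effect of unequal early stopping.** Suppose a share d of the 18 mg arm stops at Day s, every placebo patient completes, and the event rate is constant. All three are assumptions. The loss in events per patient is d × (85 − s)/92:

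- 25% at Day 30: 0.25 × 55/92 = 14.9%
- 15% at Day 40: 0.15 × 45/92 = 7.3%
- 33% at Day 20: 0.33 × 65/92 = 23.3%

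In the first case a true rate ratio of 1.5 against PBO2 would appear as 1.5 × (1 − 0.149) = 1.28 in events per patient, and as 3 × 1.28 = 3.83 in raw counts.

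**Which denominator.** The SAP 7.1 patient-years end at the last dose, while TEAEs are counted for 7 more days. In the 25%, Day 30 case, mean treatment is 85 − 13.75 = 71.25 days and mean time at risk is 92 − 13.75 = 78.25 days. Using the 7.1 patient-years would multiply the rate ratio by (78.25/71.25)/(92/85) = 1.015. The mismatch is small, but using the right window avoids it.

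**The case against.** The case on the other side has several parts.

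- **Safety is descriptive.** Protocol 5.9 sets no test or threshold. The same endpoint carries a percentage that allocation does not affect, and SAP 13.2.4 puts N in every column heading, so a reader can divide. This stands and limits the severity. It does not cover unequal time at risk, which N cannot correct.
- **Early stopping does not hide intolerant patients.** A reader might infer that early stopping makes the percentage of patients with a TEAE look too low. The documents do not support that for overall incidence: a patient who stops because of a TEAE is already counted. Later, different preferred terms may be lost. Intolerance is also visible in the table of AEs leading to study drug discontinuation (SAP 7.2) and in the reasons for stopping treatment (SAP 6.1).
- **The threefold factor is not general.** It holds against PBO2 only; against Overall placebo it is 1.64.
- **The stopping scenario is assumed.** No discontinuation rate is given, and Protocol 3.5.4.3 provides for dose reduction where a dose is not tolerated. SAP 7.2 lists Weeks 1, 2 and 5 separately to look for effects of each dose step. If events cluster early, fewer are lost than calculated, and a patient-year rate could overstate the hazard in early stoppers. This stands.
- **Absence is not proved.** Table detail is in a separate shell document (SAP 2), and the table index is not in the text available. A rate table there cannot be ruled out, but the SAP text specifies none.

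**Conclusion.** The point holds as a moderate gap in the analysis plan. A raw event count is part of the primary endpoint and is to be compared with placebo, yet with no drug effect it would differ by factors of 3.0, 1.64 and 3.6 depending on the comparator. Those factors rest only on the planned allocation and equal exposure.

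The early-stopping effect is conditional. It is about 15% fewer events per patient on 18 mg in the central scenario, and 7% to 23% for 15% to 33% stopping at Day 40 to Day 20, given a constant event rate and no placebo stopping. It is less if events cluster early.

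The stronger conclusion, that the primary safety analysis as a whole is biased toward making 18 mg look safe, does not follow. The percentage of patients with at least one TEAE is independent of allocation and still includes those who stop because of a TEAE.

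**What to change.** In SAP 7.2, keep the crude counts and percentages and add beside them:

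1. The event rate per patient-year by arm for TEAEs, study drug-related TEAEs and AESIs. Time at risk runs from first dose to last dose + 7 days, not the 7.1 patient-years that end at the last dose.
2. For on-therapy SAEs, the same rate with time at risk through 28 days after the last dose, truncated at last contact, to match SAP 5.2.4.
3. An 18 mg versus PBO2 rate ratio with 95% CI for the overall categories only, using a variance that allows for repeated events within a patient. PBO2 offers only about 12 × 92/365.25 = 3.0 patient-years, so rates by SOC and PT should stay descriptive.

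The cost is SAP wording and extra columns; the dosing and event dates are already collected. The downside is that a patient-year rate assumes a roughly constant hazard, so it supplements the crude incidence and does not replace it.
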